9.4.6. Follow-up

Adverse event information will be collected until the patient's last study visit.

Serious adverse event information will be collected until the event is considered chronic and/or stable.

9.5. Evaluation of Severity and Causality

9.5.1. Evaluation of Severity

The severity of AEs will be graded according to the following scale:

- **Mild:** Does not interfere in a significant manner with the patient normal functioning level. It may be an annoyance. Prescription drugs are not ordinarily needed for relief of symptoms, but may be given because of personality of the patient.
- **Moderate:** Produces some impairment of functioning but is not hazardous to health. It is uncomfortable or an embarrassment. Treatment for symptom may be needed.
- **Severe:** Produces significant impairment of functioning or incapacitation and is a definite hazard to the subject's health. Treatment for symptom may be given and/or patient hospitalized.

If a laboratory value is considered an AE, its severity should be based on the degree of physiological impairment the value indicates.

Injection Site Reactions

The severity of injection site reactions will be graded according to the following scale (semi-colon indicates "or" within description of grade):

- **Mild:** Pain that does not interfere with activity; mild discomfort to touch; <5 cm of erythema or induration that does not interfere with activity
- **Moderate:** Pain that requires repeated use of non-narcotic pain reliever >24 hours or interferes with activity; discomfort with movement; 5.1 cm to 10 cm erythema or induration or induration that interferes with activity
- **Severe:** Pain that requires any use of narcotic pain reliever or that prevents daily activity; significant discomfort at rest; >10 cm erythema or induration; prevents daily activity; requires emergency room visit or hospitalization; necrosis or exfoliative dermatitis.

9.5.2. Evaluation of Causality

Relationship of Adverse Events to Study Drug:

The relationship of AEs to study drug will be assessed by the "blinded" investigator, and will be a clinical decision based on all available information. The following question will be addressed:

Is there a reasonable possibility that the AE may have been caused by the study drug?

The possible answers are:

Not Related: There is no reasonable possibility that the event may have been caused by the study drug.

Related: There is a reasonable possibility that the event may have been caused by the study drug.

The investigator should justify the causality assessment of each SAE.

A list of factors to consider when assessing the relationship of AEs to study drug is provided below:

Relationship of Adverse Events to Injection Procedure or Study Procedure:

The relationship of AEs to injection procedure or study procedure will be assessed by the "blinded" investigator, and will be a clinical decision based on all available information. The following question will be addressed:

Is there a reasonable possibility that the AE may have been caused by the injection procedure or study procedure?

The possible answers are:

Not Related: There is no reasonable possibility that the event may have been caused by the injection procedure or study procedure.

Related: There is a reasonable possibility that the event may have been caused by the injection procedure or study procedure.

The sponsor will request information to justify the causality assessment of SAEs, as needed.

A list of factors to consider when assessing the relationship of AEs to injection procedure or study procedure is provided below.

Factors to Consider in Assessing the Relationship of AEs to Study Drug, Injection Procedure, or Study Procedure:

Is there a reasonable possibility that the event may have been caused by the study drug, injection procedure, or study procedure?

No:

- due to external causes such as environmental factors or other treatment(s) being administered
- due to the patient's disease state or clinical condition
- do not follow a reasonable temporal sequence following the time of administration of the dose of study drug or injection procedure, study procedure, or background treatment, etc.
- do not reappear or worsen when dosing with study drug or injection procedure, study procedure, or background treatment, etc. is resumed
- are not a suspected response to the study drug or injection procedure, study procedure, or background treatment, etc. based upon preclinical data or prior clinical data

Yes:

- could not be explained by environmental factors or other treatment(s) being administered
- could not be explained by the patient's disease state or clinical condition

- follow a reasonable temporal sequence following the time of administration of the dose of study drug or injection procedure, study procedure, or background treatment, etc.
- resolve or improve after discontinuation of study drug or injection procedure, study procedure, or background treatment, etc.
- reappear or worsen when dosing with study drug or injection procedure, study procedure, or background treatment, etc. is resumed
- are known or suspected to be a response to the study drug or injection procedure, study procedure, or background treatment, etc. based upon preclinical data or prior clinical data

NOTE: This list is not exhaustive.

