10.4.4.1. Adverse Events

Definitions

For safety variables, 3 observation periods are defined:

- The pretreatment period is defined as the time from signing the ICF to before the first dose of study drug.
- The on-treatment period is defined as the day from first dose of study drug to the day of the last dose of study drug (week 12) + 4 weeks.
- The follow up period is defined as the time from the end of the on-treatment period (week 16) to the week 36 visit.

Treatment-emergent adverse events are defined as those that are not present at baseline or represent the exacerbation of a pre-existing condition during the on-treatment period.

Analysis

All AEs reported in this study will be coded using the currently available version of the Medical Dictionary for Regulatory Activities (MedDRA[®]). Coding will be to lowest level terms. The verbatim text, the preferred term (PT), and the primary system organ class (SOC) will be listed. The focus of adverse event reporting in the clinical study report will be on TEAEs. Post treatment AEs and all AEs during the study will be summarized similarly as TEAEs.

Summaries of all TEAEs by treatment group will include:

- The number (n) and percentage (%) of patients with at least 1 TEAE by SOC and PT
- TEAEs by severity (according to the grading scale outlined in Section 9.5.1), presented by SOC and PT

- TEAEs by relationship to treatment (related, not related), presented by SOC and PT
- Treatment-emergent AESIs (defined with a PT or a pre-specified grouping)

Deaths and other SAEs will be listed and summarized by treatment group.

Treatment-emergent adverse events leading to permanent treatment discontinuation will be listed and summarized by treatment group.

In addition, AESIs will be reported according to the adjudicated diagnosis. Imaging data related to AA including change from baseline in joint space width will be summarized.

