At the time of the study drug discontinuation, 63 patients had been randomized into the study. Patients will be encouraged to remain in the study and be followed for the off-treatment period study visits until completion of the study to continue to monitor safety for patients that were randomized.

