### **5.9.2. Adverse Events**

The verbatim text, the preferred term, and the primary SOC will be listed in patient listings. Summaries that include frequencies and proportions of patients reporting AEs will include the preferred terms and the SOCs.

- *Pre-Treatment Adverse Events* are defined as AEs that developed or worsened during the pre-treatment period.

- *Treatment-Emergent Adverse Events (TEAE)* are defined as those that are not present at baseline or represent the exacerbation of a pre-existing condition during the on-treatment period.
- *Post-Treatment Adverse Events* are defined as AEs that developed or worsened more than 28 days after the last dose of study drug.

The focus of adverse event reporting in the clinical study report will be on TEAEs. Post-treatment AEs and AEs during the study will be summarized similarly as TEAEs.

Summaries of TEAEs by treatment group will include:

- Overview of TEAEs, summarizing number of events, summarizing number and percentage of patients within the specified category
  - Total number of TEAEs
  - Total number of Serious TEAEs
  - Patients with any TEAEs
  - Patients with any Serious TEAEs
  - Patients with any TEAEs leading to death
  - Patients with any TEAEs leading to withdrawal from study
  - Patients with any TEAEs leading to permanent study treatment discontinuation
- All TEAEs by SOC and PT
- All TEAEs by SOC, PT, severity
- Study drug related TEAEs by SOC and PT
- TEAEs resulting in Permanent Study Drug Discontinuation by SOC and PT
- AESI by SOC and PT
- Serious TEAEs by SOC and PT

Listing to include:

- Listing of AEs leading to death
- Listing of TEAEs leading to permanent study treatment discontinuation
- Listing of TEAEs leading to withdrawal from study
- Listing of Patients with Serious TEAEs
- Listing of Patients with AESIs
- Listing of all Joint Replacements

Counts will be provided according to treatment group for each PT within each primary SOC. Percentages will be calculated based on the SAF in each treatment group.

Primary SOCs will be sorted by decreasing frequency in the fasinumab group. Within each primary SOC, PTs will be sorted by decreasing frequency in the fasinumab group. For tables presenting severity of events, the worst severity will be chosen for patients with multiple instances of the same event.

TEAEs with preferred terms  $\geq 5\%$  in any treatment group will be summarized in the report.

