### ***Handling of Adverse Event and Injection Site Reaction Severity and relatedness***

If the severity of a TEAE is missing, it will be classified as “severe” in the frequency tables by severity of TEAEs.

If the assessment of relationship of a TEAE to the study drug or study conduct is missing, it will be classified as “related” to the investigation product.

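### SAP 6.3 lets a missing procedure-causality answer make a TEAE drug-related, even when the investigator has recorded it as not related to study drug

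*Protocol*

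**What the plan says.** Protocol 9.5.2 sets two causality questions, both for the blinded investigator and each with its own related or not-related answer. The first is "Is there a reasonable possibility that the AE may have been caused by the study drug". The second is "Is there a reasonable possibility that the AE may have been caused by the injection procedure or study procedure". The protocol treats them as separate assessments and has no third.

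SAP 6.3, in the paragraph on missing severity and relatedness, has one rule for missing causality. The trigger is "If the assessment of relationship of a TEAE to the study drug or study conduct is missing". The result is "it will be classified as “related” to the investigation product". No condition protects a study-drug answer that has been recorded.

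The classification feeds "Study drug related TEAEs by SOC and PT" in SAP 5.9.2. The matching item in Protocol 10.4.4.1 is "TEAEs by relationship to treatment (related, not related), presented by SOC and PT". SAP 5.9.2 lists no table of procedure-related TEAEs, and its overview of TEAEs has no relatedness row.

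**The concern.** Treating a missing answer as the worst case is ordinary practice when the default fills the field that is missing. This rule goes further. It has two triggers and one outcome, so a blank in the procedure field decides the study-drug classification even when the study-drug question has been answered.

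What is at stake is the meaning of the drug-related table. A reader takes it to show events that the investigator attributed to study drug, plus those with no attribution recorded. Under the literal rule it also holds events that the investigator said were not drug-related, in numbers that depend on how completely another field was filled in.

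The study stopped early and has no efficacy hypothesis tests (SAP 5.8), so its safety summaries carry much of what the report can offer. That is a reason to get a small point right. It does not make the point large.

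**Working it through.** The plan gives no figure to reproduce. The check compares the texts, with one line of arithmetic for scale.

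**Step 1. What does *study conduct* refer to?** The SAP uses the term without defining it, and the protocol does not define it either. The protocol has two causality questions, and the SAP rule names study drug separately. The remaining one, injection or study procedure, is the natural match. This is an inference from the documents, not something they state.

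**Step 2. Apply the rule to each combination of answers.**

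| Study-drug answer | Procedure answer | Class under the literal SAP rule | Comment |
|---|---|---|---|
| Recorded | Recorded | As recorded for study drug | No imputation |
| Missing | Recorded | Drug-related | Ordinary conservative default |
| Missing | Missing | Drug-related | Ordinary conservative default |
| Recorded as related | Missing | Drug-related | Class unchanged |
| Recorded as not related | Missing | Drug-related | Recorded answer overridden |

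Only the last row is a misclassification.

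**Step 3. Compare the neighbouring rules in SAP 6.3.** The severity rule fills a missing severity and touches nothing else. The rule for incomplete AE dates defaults to treatment-emergent but gives way when a partial date clearly places the onset before treatment. In both, recorded information stands. The relatedness rule is the exception.

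**Step 4. Scale.** The only count available is "At the time of the study drug discontinuation, 63 patients had been randomized into the study". SAP 5.9.2 bases percentages on the safety analysis set, which SAP 3.2 limits to randomized patients who received study drug. Neither its size nor the split by arm is given. Assume that nearly all 63 were treated and that the 1:1 allocation left 31 or 32 per arm. One patient newly added to a row then moves that arm's percentage by:

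- 100 × 1/32 = 3.1 percentage points
- 100 × 1/31 = 3.2 percentage points

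With fewer treated patients the step, 100/n, is larger. A patient already counted in the row adds nothing, because the table counts patients, not events.

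**The case against.** The strongest reply is that the rule is shorthand. It speaks of the assessment in the singular and may have been meant to say that whichever assessment is missing defaults to related for its own question. For a drug-related table, a programmer might simply use the study-drug answer. Intent may well have been that. But the text names only the investigational product as the outcome, and SAP 5.9.2 has no procedure table for the second trigger to feed, so a programmer who follows the SAP as written would code the override.

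A second reply is that procedure answers should rarely be missing. Protocol 12.3 makes the investigator responsible for complete CRFs, 12.1 has monitors verify completeness, and 11.1 provides for validation and cleaning. This stands as a limit on size: a missing rate of zero is fully compatible with the documents. It does not make the rule correct when a blank does occur.

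A third reply is that the rule errs on the safe side and applies equally to both arms under blinded assessment. That also stands, and it is why the point is minor.

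Two stronger readings are tempting and are not supported:

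- A reader might assume that some share of TEAEs, say 2% to 10%, lack the procedure answer, and infer that the same share become drug-related. The documents give no such rate. Even with that assumption the figure is only an upper bound. Events already recorded as drug-related do not change class, and events with no study-drug answer would be classed as related under any sensible default.
- A reader might infer that the safety comparison between arms is distorted. Drug-related TEAEs are not among the safety endpoints in SAP 4.5.1, and no formal comparison of them is specified. Overall TEAE incidence, adjudicated and destructive arthropathy, sympathetic nervous system dysfunction, joint replacement and all efficacy summaries do not use this rule.

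**Conclusion.** The point holds as a minor defect in one SAP sentence. Protocol 9.5.2 is sound; the fault lies in SAP 6.3, where a single outcome is attached to two different missing fields. Taken literally, the rule puts a TEAE recorded as not related to study drug into the drug-related table when only the procedure answer is blank. No other section corrects this.

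The conclusion rests on reading *study conduct* as the protocol's procedure question. If it was meant to be something else, the term still needs a definition.

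The effect is limited to the descriptive drug-related summary, can only over-count, and operates in both arms. Its size depends on a missing rate that the documents do not give and that may be zero. The figure of about 3 percentage points per newly counted patient holds only if the treated set is close to the 63 randomized and split about evenly.

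**What to change.** In SAP 6.3, replace *study conduct* with the protocol's term, injection procedure or study procedure, and state the imputation field by field:

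- A missing study-drug relationship is classified as related to study drug.
- A missing procedure relationship is classified as related to the procedure only.
- A recorded study-drug answer is never changed because another causality field is missing.

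The cost is a sentence or two of SAP text and a small change to the derivation, with no new data. SAP Section 1 already allows revisions based on blinded review before database lock.

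The conservative default remains where the study-drug answer itself is missing. The corrected table will therefore hold events recorded as drug-related plus events with no study-drug answer. Its counts can fall or stay the same, but they will not necessarily equal what investigators recorded as related.

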9.6. Safety Monitoring

The investigator will monitor the safety of study patient at his/her site(s) as per the requirements of this protocol and consistent with current Good Clinical Practice (GCP). Any questions or concerns should be discussed with the sponsor in a timely fashion. The sponsor will monitor the safety data from across all study sites. The medical monitor will have primary responsibility for the emerging safety profile of the compound, but will be supported by other departments (eg, Pharmacovigilance and Risk Management; Biostatistics and Data Management). Safety monitoring will be performed on an ongoing basis (eg, individual review of SAEs) and on a periodic cumulative aggregate basis.

Any patient whose study drug is discontinued due to an AA should be encouraged to return to the clinic for all remaining study visits. If JR surgery is warranted, prior to the scheduled JR, the patient should complete the pre-operative study visit and, after the JR, should complete the week 4 and week 20 post-operative study visits (Section 8.2.3.5, Table 1). Pre-operative images, along with any other radiographic evaluation will be submitted to the Adjudication Committee for review (Section 5.3.2).

Details of data collection for adjudication of events will be provided in the adjudication charter.

9.6.1.2. Sympathetic Nervous System Dysfunction

Sympathetic nervous system dysfunction will be monitored throughout the study through physical examination, AE reporting, assessment of orthostatic hypotension, and the Survey of Autonomic Symptoms (Section 8.2.2.5). New onset or worsening of signs and symptoms of autonomic dysfunction will be evaluated by the investigator. Sympathetic nervous system dysfunction will only be diagnosed after consultation with an appropriate specialist, such as a neurologist and/or cardiologist.

In cases in which new or worsening symptoms consistent with SNS dysfunction are moderate-to-severe or are clinically significant and do not resolve or return to baseline in 2 weeks (or less at the discretion of the investigator), study drug will be withheld and the patient will be referred to a specialist. If the evaluation by the appropriate specialist does not suggest SNS dysfunction, study drug may be restarted. If the specialist's evaluation does reveal SNS dysfunction then study drug will be permanently discontinued and the case will be reported as an AESI (Section 9.4.3).

Orthostatic hypotension may be a manifestation of SNS dysfunction. If a patient is determined to have orthostatic hypotension, study drug should be withheld and the AE should be entered in the CRF. The following procedures should be followed:

- If the patient is symptomatic and a clinical explanation for orthostatic hypotension is identified (such as a new medication or dehydration due to exercise or illness or excessive heat exposure), study drug will be withheld, and the patient should return to the study site for an unscheduled visit in 1 to 10 days for an unscheduled assessment of orthostatic hypotension.
 - If the orthostatic hypotension has resolved, study drug may be restarted.
 - If the orthostatic hypotension has not resolved, then study drug will be withheld, and the patient will be referred to a specialist (neurologist or a cardiologist) for evaluation of SNS dysfunction.
 - If the specialist's evaluation does not reveal new onset SNS dysfunction, including symptoms of bradycardia (lightheadedness), orthostatic hypotension (lightheadedness on standing), syncope, absence of sweating in conditions where sweating would be expected, or if the specialist's evaluation identifies an alternative cause, such as initiation of a new medication known to cause orthostasis, then study drug may be given at the next visit.
 - If the specialist's evaluation does reveal SNS dysfunction, then study drug will be permanently discontinued and the case reported as an AESI (Section 9.4.3).
- If the patient has asymptomatic orthostatic hypotension, study drug will be withheld, and the patient should return to the study site for an unscheduled visit in 1 to 10 days for an unscheduled assessment of orthostatic hypotension.
 - If the unscheduled assessment does not reveal orthostatic hypotension then study drug may be continued.
 - If the unscheduled assessment demonstrates orthostatic hypotension then study drug will continue to be withheld until the patient has been evaluated by a specialist (neurologist or a cardiologist) for evidence of SNS dysfunction.
 - If the specialist's evaluation does not reveal new SNS dysfunction including symptoms of bradycardia (lightheadedness), orthostatic hypotension (lightheadedness on standing), syncope, absence of sweating in conditions where sweating would be expected, or if the specialist's evaluation identifies an alternative cause such as initiation of a new medication known to cause orthostasis, then study drug may be restarted.
 - If the specialist's evaluation does reveal SNS dysfunction then study drug will be permanently discontinued and the case reported as an AESI (Section 9.4.3).

9.6.1.3. Peripheral Sensory Adverse Events

Altered peripheral sensation (eg, paraesthesia and hypoaesthesia) is an important identified risk with fasinumab (see Investigator's Brochure) and other anti-NGF compounds. Any peripheral sensory AE that, per the investigator's judgment, requires a neurology consultation must be reported as an AESI. If any peripheral sensory event persists for 2 months the patient must be referred for a neurology consultation and the event must be reported as an AESI.

